2.3 Exploratory

The exploratory objectives of this study are:

- To determine the effect of SUBLOCADE administered in the ED, inpatient unit or in the clinic within 7 days (168 h) of an opioid OD followed by SUBLOCADE administration monthly on the amount of opioid craving.
- To determine the efficacy of SUBLOCADE administered in the ED, inpatient unit or in the clinic within 7 days (168 h) of an opioid OD followed by SUBLOCADE in the clinic on opioid use as determined by Urine Drug Screen (UDS).
- To evaluate the effect of SUBLOCADE administered in the ED, inpatient unit or in the clinic within 7 days (168 h) of an opioid OD followed by SUBLOCADE in the clinic in the clinic on decision making using a delay discounting task and a brief opioid demand measure to measure craving valuation (hypothetical maximum price participants would be willing to pay for access to opioid, assessing craving/valuation).
- To evaluate the association between participant genetic polymorphisms and subjects with history of OD in subjects that consent to the PGx sub-study.
- To evaluate the relationship between genetics/behavioural laboratory measures of decision making and treatment outcome, including repeat OD in subjects that consent to the PGx sub-study.
- To determine the relationship between decision making and treatment retention and illicit opioid use.
- To evaluate healthcare resource utilisation associated with either treatment regimen as compared to the controls (2015-to end of data collection period) obtained from VCU anonymized health records.
- To assess the impact SUBLOCADE administered in the ED, inpatient unit or in the clinic within 7 days (168 h) of an opioid OD followed by administration of SUBLOCADE in

the clinic on treatment effectiveness as measured by Treatment Effectiveness Assessment (TEA), on medication satisfaction as measured by the Medication Satisfaction Questionnaire (MSQ), and on employment, presentism and absenteeism as assessed by the Work Productivity and Activity Impairment Questionnaire: Specific Health Problem (WPAI:SHP).

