3.3 Exploratory

The exploratory endpoints of this study are:

- Opioid craving in subjects as measured by Craving Visual Analog Scale (VAS) scores.
- Illicit opioid use as measured by urine drug screen (UDS) results.
- Genetic predictors of treatment response and OD.
- Predictability of treatment response based on impulse control as measured by decision making in the delay discounting task, and opioid cravings/valuation as measured by the brief opioid demand task.
- Numbers of ED and hospital visits compared to the historical control (2015-2018) obtained from VCU anonymized health records.
- Scores on Treatment Effectiveness Assessment (TEA), medication satisfaction as measured by the Medication Satisfaction Questionnaire (MSQ), and employment, presentism and absenteeism as assessed by the Work Productivity and Activity Impairment Questionnaire: Specific Health Problem (WPAI:SHP).

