8.9.2 Healthcare Resource Utilization Questionnaire (HCRUQ)

The HCRUQ will be completed by the Investigator or qualified designee and will collect hospitalizations; residential substance abuse treatment; general practitioner, specialist, and counselling visits; and Emergency Department (ED) visits. Also, The HCRUQ information will be obtained from informatics and electronic medical records from the respective site. It will

include information on medical services provided in the inpatient, outpatient, emergency department and other ancillary services available within the site's network.

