The probabilities for the control cohort will be used as weights in the Cox proportional hazards model. The weights serve to make the control cohort appear similar to the treatment group on the observed baseline characteristics; this will be checked using covariate balance diagnostics. The weights will provide greater weight for control patients who likely would have participated if offered a prospective trial of SUBLOCADE and lesser weight for patients unlikely to have consented.

In addition, the results will be illustrated with a Kaplan-Meier curve.

The analysis will take place once all subjects have completed the trial and sufficient time has passed to allow the state death registries to be updated.

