14.7.2.1 Health Economics & Outcomes Analyses

Treatment Effectiveness Assessment (TEA)

HEOR endpoints relating to the TEA will be described as change from baseline score to each follow-up assessment and end of treatment (EOT). Absolute scores by study visit will also be reported and compared between treatment groups. The absolute score and/or change from baseline score at EOT will be considered the primary variable of interest in these analyses.

Baseline will be defined as the last assessment on or before Week 3 Day 15±4 (Visit 4). (See Appendix 2- Treatment Clinic Schedule of Events)

MEDICATION SATISFACTION QUESTIONNAIRE (MSQ)

The percentage of subjects reporting each response on the MSQ will be reported by study visit and EOT. The percentage of subjects reporting that they are satisfied (score 5-7) at the EOT will be considered the primary variable of interest in these analyses.

WORK PRODUCTIVITY ASSESSMENT INSTRUMENT: SPECIFIC HEALTH PROBLEM (WPAI:SHP)

For the WPAI:SHP, the percentage of patients employed, percentage absenteeism, percentage work impairment, and percentage activity impairment will be reported at baseline, each follow-up assessment and EOT by treatment arm. The change in percent employed from baseline to each follow-up assessment will be assessed. Among those employed at baseline and the respective follow-up assessments, the changes from baseline in percentage absenteeism, percentage work impairment and percentage activity impairment at each follow-up assessment will be assessed. The change in percent employed from baseline to EOT; and among those employed at baseline and EOT, the changes in percentage absenteeism, percentage work impairment and percentage activity impairment from baseline to EOT will be considered as primary variables of interest in these analyses.

Baseline will be defined as the last assessment on or before Week 3 Day 15±4 (Visit 4). (See Appendix 2- Treatment Clinic Schedule of Events)

HEALTHCARE RESOURCE UTILIZATION QUESTIONNAIRE(HCRUQ)

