Frequency of use by HCRUQ type will be summed throughout the study period, from Week 1 to EOT (or last visit with available data for subjects who discontinue treatment prematurely), to arrive at a total use while in the study. The incidence of HCRUQ by type will be assessed, dividing by the total amount of follow-up time in each group. Types of hospitalisations, emergency room, and outpatient service visits will be categorized (e.g., medical, surgical, psychiatric). Hospital days will be calculated as the sum of all inpatient days during the study.

For continuous measures, 95% confidence intervals will be provided for comparisons of statistics between treatments. Unless otherwise specified, the absolute value of continuous outcome measures will be analysed using a mixed model for repeated measures (MMRM). A test of proportions (for example: exact test) will be used to evaluate treatment differences for categorical outcome variables.

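### The exploratory comparison of healthcare use with VCU record controls has no case-mix adjustment and no rule for the index episode, so a difference may partly reflect who was treated and what was counted

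*Combined protocol and SAP*

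**What the plan says.** **Comparator and scope.** Section 3.3 lists as an exploratory endpoint "Numbers of ED and hospital visits compared to the historical control (2015-2018) obtained from VCU anonymized health records". The Synopsis, in its exploratory objectives and endpoints, and Section 2.3 speak of healthcare resource utilisation in general. Section 2.3 also gives a different control window: "as compared to the controls (2015-to end of data collection period) obtained from VCU anonymized health records".

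**Counting.** Section 14.7.2.1 states: "Frequency of use by HCRUQ type will be summed throughout the study period, from Week 1 to EOT", or to the last visit with data for those who stop early. Section 8.9.2 says that the questionnaire "will collect hospitalizations; residential substance abuse treatment; general practitioner, specialist, and counselling visits", as well as ED visits, and that site electronic records will supply the information too.

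**Analysis.** Section 14.7.2.1 continues: "The incidence of HCRUQ by type will be assessed, dividing by the total amount of follow-up time in each group". It plans 95% confidence intervals and MMRM for continuous measures. For the rest, "A test of proportions (for example: exact test) will be used to evaluate treatment differences for categorical outcome variables".

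**Adjustment elsewhere.** Section 14.7.1 gives treated subjects weight 1 and controls p/(1-p) for time to repeat overdose or opioid-related death. Its reason is that "The weights serve to make the control cohort appear similar to the treatment group on the observed baseline characteristics".

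**Patient-reported outcomes.** For the TEA, Section 14.7.2.1 says: "Absolute scores by study visit will also be reported and compared between treatment groups".

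**The concern.** Section 14.7.1 accepts that VCU controls and consenting subjects differ at baseline and that the contrast needs weighting. Healthcare use is set against controls from the same source with no weight, match or covariate. A lower or higher ED or hospital rate in treated subjects could then arise partly from who consented.

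The count also has no stated starting rule. For subjects who start SUBLOCADE in the ED or inpatient unit, Week 1 Day 1 falls within the index episode. For clinic starters it does not, because they may present up to 7 days after the overdose and some were seen only by EMS. Controls are selected by an ED overdose visit (Section 6.1). Unless the index episode is handled alike in all of them, the rates are not on one footing.

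At stake is the reading of a published healthcare-use result as a drug effect.

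**Working it through.** The documents give no rate, power or alpha for healthcare use, so there is no plan figure to reproduce. All background rates and prevalences below are assumptions. The sizes 99 and 198 are borrowed from Section 14.2, where they serve the primary endpoint.

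**1. Is any adjustment specified?** Section 14.7.1 confines propensity analysis to repeat overdose or opioid-related death. Table 2 in Section 14.7.2 names propensity scores in that row only and has no healthcare-use row. Section 14.7.2.1 names no weight or covariate for rates, MMRM or tests of proportions. So none is specified.

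**2. Case mix, rate ratio.** If a factor multiplies use by R and is present in a fraction q1 of treated and q0 of controls, then with no drug effect the crude ratio is [1 + q1(R-1)] / [1 + q0(R-1)].

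| R | q1 | q0 | Crude ratio |
|---|---|---|---|
| 2 | 0.6 | 0.3 | 1.6/1.3 = 1.23 |
| 2 | 0.3 | 0.6 | 1.3/1.6 = 0.81 |
| 2 | 0.4 | 0.5 | 1.4/1.5 = 0.93 |
| 3 | 0.3 | 0.5 | 1.6/2.0 = 0.80 |

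**3. Case mix, exact test.** Two-sided Fisher test at 5%, 99 treated and 198 controls, no drug effect. The treated proportion with any use is lower than the control proportion through case mix alone. Entries are the probability of rejection.

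| Control proportion | Gap 0 | 5 points | 10 points | 15 points |
|---|---|---|---|---|
| 20% | 4.2% | 15.6% | 58.2% | 96.4% |
| 30% | 4.3% | 12.8% | 43.0% | 81.9% |
| 40% | 4.5% | 12.5% | 38.0% | 72.4% |

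**4. Index episode.** Appendix 2 puts EOT at Day 169, so follow-up is 169/365.25 = 0.463 years. One index ED visit adds 1/0.463 = 2.16 visits per person-year. If it is counted for ED starters and not for controls, the apparent ratio among ED starters is (b + 2.16)/b for a background of b visits per person-year:
- b = 1: 3.2
- b = 2: 2.1
- b = 4: 1.5

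If only half of the treated group were ED starters, the addition would be 1.08, and the ratio would be 2.1 at b = 1 and 1.3 at b = 4. If the visit were counted for controls but not for treated subjects, the error would run the other way.

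**5. Scheduled visits, broad wording only.** Appendix 2 marks counselling at Visits 2-11 (10), Visits 12-19 (8) and EOT (1), which makes 19. That is 19/169 x 30 = 3.4 per 30 days, or 19/0.463 = 41 per person-year. If these were counted against assumed backgrounds of 2 and 12 outpatient visits per person-year, the apparent ratios would be (2 + 41.06)/2 = 21.5 and (12 + 41.06)/12 = 4.4. They do not enter a count of ED and hospital visits.

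**6. Comparator for scores.** There is one open-label treated arm. Section 13.1.1 describes controls as an anonymised record extract. No control has a TEA, MSQ or WPAI score.

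**The case against.** The strongest reply is that Section 3.3 already restricts the control comparison to ED and hospital visits. A reader might infer that the scheduled counselling visits inflate the comparison by design. The documents do not support that: under Section 3.3 these visits drop out, and Section 14.7.2.1 neither includes nor excludes them. What stands is that the Synopsis and Section 2.3 use broader wording, which should be reconciled with Section 3.3.

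A reader might also take Day 1 to be the index encounter for everyone. It is not so for clinic starters. Appendix 1 has no questionnaire at Visit 1; the first is at Visit 2. Whether the index episode is counted is therefore unstated, not settled either way.

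The plan is not confined to crude rates and exact tests, since MMRM and confidence intervals are also named; but those too are unweighted. The sentence on tests of proportions closes the whole health-economics section and does not itself mention VCU controls. The link comes from the objectives and endpoints. Nor is treated use taken only from a questionnaire, because Section 8.9.2 also draws on site records, so a common source is within reach.

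On patient-reported outcomes, it would be too strong to say that the whole plan cannot be run. Change from baseline is already planned for TEA and WPAI, and MSQ is reported as percentages. The explicit group comparison is for TEA, with general between-treatment wording for the section as a whole. That wording may be left over, or may refer to the setting in which treatment began.

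Finally, weighting is no cure-all. The listed predictors are examples such as age, gender, county, race and insurance status, and an unmeasured driver of ED use would remain.

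**Conclusion.** The concern holds in a limited form. No case-mix adjustment is specified for healthcare use against VCU controls, and no rule covers the index episode. A difference may partly reflect case mix and counting. The documents do not show that it must, or how much of it would.

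The illustrations give a crude ratio of 0.80 to 1.23 from one unbalanced factor, and a rejection probability of 38-58% for a 10-point gap with no drug effect. Both rest on assumed inputs. The index-episode ratios of 1.5 to 3.2 assume that the visit is counted only for ED starters. The scheduled-visit ratios of 4.4 to 21.5 apply only if the broad wording governs and those visits are counted.

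The TEA group comparison, and any between-treatment test of MSQ or WPAI against controls, has no comparator. The endpoint is exploratory, so the primary and key secondary results are unaffected.

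**What to change.** In Section 14.7.2.1:

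- Make ED visits and hospital stays, the Section 3.3 endpoint, the control comparison. Take them from VCU electronic records in both groups, counted after the index episode from a common time zero and over the same window.
- Analyse them with a weighted Poisson or negative binomial model, log follow-up time as offset and robust standard errors. Build the weights as in Section 14.7.1 (treated 1, controls p/(1-p)) and re-estimate them if the control set differs from that of the primary analysis.
- Reconcile the 2015-2018 window of Section 3.3 with the longer window of Section 2.3, and align the general utilisation wording with the chosen endpoint.
- Report outpatient, counselling and questionnaire-only use descriptively for treated subjects.
- For TEA, MSQ and WPAI, replace between-group wording with within-subject change or percentages and 95% confidence intervals.

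The cost is SAP wording and, at most, one further fit of the propensity model. Out-of-network use is left out of the comparison, and the weights adjust only for measured characteristics.

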14.7.3 Exploratory Analysis

Genetic predictors of treatment response and outcomes analysis will include a study of polymorphisms in candidate pharmacokinetic and pharmacodynamic genes in subjects that consent to the optional PGx sub-study with an aim of understanding the role of genetic variants in modifying the risk of future OD and to determine treatment outcomes. This analysis will include all subjects that consented to participate in the PGx sub-study.

The predictability of treatment response based on impulse control analysis will be performed using logistic regression models predicting treatment success (e.g., point prevalence opioid abstinence, treatment retention) as a function of baseline delay discounting, and opioid craving/valuation. Additionally, possible changes in delay discounting and craving/valuation over the course of treatment will be modelled using repeated measures analysis of covariance (ANCOVA), including time as a within-subjects factor, and relevant demographic and substance use measures as covariates. This analysis will be performed using the treatment population.

14.7.4 Subgroup Analysis

Primary analyses will be repeated but adding an explanatory class variable of subjects identified as injectors vs. non-injectors at Week 1 Day 1 (Visit 1).

14.8 Handling of Missing Data

In general, missing data (caused by premature discontinuation or otherwise) will not be imputed. However, missing urine drug screen data will be imputed based on previously defined methods in other patient populations. The secondary endpoint is time attending clinic and patients failing to appear will be considered to have stopped attending at the date of last visit after they've missed 5 consecutive visits. Any missing covariates will be handled via appropriate multiple imputation techniques.

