Once subjects are engaged in care at the treatment clinic, they will continue to receive SUBLOCADE for 6 months. The second 300 mg injection will be administered on Day 8 (-0/+4 days) after the first injection, with subsequent 300 mg injections administered at 28-day (-2/+4 days) intervals over approximately 6 months for a total of 7 injections. If necessary, for tolerability, the dose of SUBLOCADE can be reduced to 100 mg. All subjects will receive site standard psychosocial therapy at least weekly during the first 3 months of treatment, and twice monthly thereafter if clinically stable.

All subjects will complete an End of Treatment (EOT) / Early Termination (ET) visit 28 days after their last injection of SUBLOCADE. Within 3 months prior to or at the EOT visit, the Investigator or a medically qualified sub-investigator will discuss the subject's available treatment options and arrange referral. All subjects will receive a safety follow-up telephone call, 30 days after their EOT/ET visit to assess AEs, SAEs, pregnancy status (if applicable) and concomitant medications. Subjects who decline to continue in medication assisted treatment (MAT) will receive monthly safety follow-up phone calls for an additional 5 months (6 months total) to assess SAEs, pregnancy status (if applicable) and concomitant medications.

Primary Endpoint(s):

The primary endpoint of this study is:

- Time to repeat OD or opioid-related death. Repeat OD or opioid-related death will be measured from electronic medical records and state death registries.
- Additional comparisons on repeat OD and death rates will be made to concurrent patients who decline to participate in the SUBLOCADE injection.

Secondary Endpoint(s):

The key secondary endpoint of the study is:

- Treatment engagement as measured by attending the outpatient clinic and receiving subsequent buprenorphine treatment at 3 and 6 months.

The secondary endpoints of this study are:

- Numbers and percent of subjects in treatment at 3 and 6 months after opioid OD.

Exploratory Endpoints:

The exploratory endpoints of this study are:

- Opioid craving in subjects as measured by Craving Visual Analog Scale (VAS) scores.
- Illicit opioid use as measured by urine drug screen (UDS) results.
- Genetic predictors of treatment response and OD.

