3.2 Secondary

The key secondary endpoints of the study are:

- Numbers and percent of patients in buprenorphine treatment at 3 and 6 months after opioid OD comparing patients who have primarily intravenous to non-intravenous opioid use.

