6.4.4 Subjects Lost to Follow-up

In cases of a missed visit, the Investigator or designee must attempt to contact the subject and re-schedule as soon as possible. The Investigator or designee must counsel the subject on the importance of maintaining the assigned visit schedule and ascertain whether or not the subject wishes to and/or should continue in the study.

In the event a subject misses 5 consecutive weeks' worth of visits, they will be considered to have ceased treatment and withdrawn from the study. Investigators or designees must make a reasonable effort to contact the subject. Two documented attempts (e.g., phone, email, etc.) to contact the subject followed by a certified mailed letter is considered reasonable. Subjects who can no longer be contacted will be considered lost to follow-up.

For the purpose of documenting date of discontinuation for a subject confirmed to be lost to follow-up, the date of discontinuation will be the date of last in-person visit.

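### The five-missed-visits rule in Section 14.8 cannot be met by anyone last seen on Day 106 or later, contradicts the five-week rule in Sections 6.4.4 and 10.1.1, and leaves these subjects' 6-month retention status undefined.

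*Combined protocol and SAP*

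**What the plan says.** Section 14.8 gives the rule for no-shows in the secondary endpoint: "patients failing to appear will be considered to have stopped attending at the date of last visit after they've missed 5 consecutive visits". The same section says "The secondary endpoint is time attending clinic" and that in general "missing data (caused by premature discontinuation or otherwise) will not be imputed".

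Section 6.4.4, repeated in Section 10.1.1, uses a different unit: "In the event a subject misses 5 consecutive weeks' worth of visits, they will be considered to have ceased treatment". For a subject confirmed lost to follow-up, Section 6.4.4 adds that "the date of discontinuation will be the date of last in-person visit".

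The endpoint itself is a status at two time points. Section 3.2 has "Numbers and percent of patients in buprenorphine treatment at 3 and 6 months after opioid OD", compared between primarily intravenous and non-intravenous users. The synopsis has "Treatment engagement as measured by attending the outpatient clinic and receiving subsequent buprenorphine treatment at 3 and 6 months". Section 14.7.2 and Table 2 analyse retention at 3 and 6 months by logistic regression in the Treatment Population without imputation. The synopsis names a Cox model.

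Appendix 2 schedules weekly visits up to Visit 15 (Day 92), then Days 106, 120, 134 and 148, then EOT on Day 169. Injections after Day 1 fall on Days 8, 36, 64, 92, 120 and 148.

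**The concern.** Five visits and five weeks are the same thing only while visits are weekly. Once they are two-weekly, five visits span about ten weeks, and the schedule ends before a late dropout can accumulate five misses. Section 14.8 then never gives that subject a stop date, while Section 6.4.4 may already have classed the same subject as having ceased treatment.

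Six-month retention is a key secondary endpoint, reported as a number and percentage. If the late dropouts have no defined status, the analyst has to choose one after the data are in, in an open-label study, and most of the available choices raise the reported figure. Any intravenous versus non-intravenous difference in dropout after Day 106 could also go unseen.

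**Working it through.** **Inputs.** Visit and injection days come from Appendix 2, and the rules from Sections 14.8, 6.4.4 and 10.1.1. I take Day 169 as the 6-month point, because Table 2 labels EOT as 6 months. I read five weeks as 35 days since the last attended visit. The documents give no retention rate for this endpoint, so there is no plan figure to reproduce.

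**Step 1: can the rule be met?** Count the scheduled visits after the last one attended.

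| Last attended | Visits left (incl. EOT) | Fifth miss falls on | Days to Day 169 | Section 14.8 | Sections 6.4.4 / 10.1.1 |
|---|---|---|---|---|---|
| Day 78 | 7 | Day 134 | 91 | stopped | ceased |
| Day 85 | 6 | Day 148 | 84 | stopped | ceased |
| Day 92 | 5 | Day 169 | 77 | stopped | ceased |
| Day 106 | 4 | never | 63 | not classed | ceased |
| Day 120 | 3 | never | 49 | not classed | ceased |
| Day 134 | 2 | never | 35 | not classed | borderline |
| Day 148 | 1 | never | 21 | not classed | not classed |

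The two rules disagree for last visits on Days 106 and 120, and possibly Day 134. Subjects last seen before Day 92 are always caught in time, so 3-month status is not affected.

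**Step 2: are these subjects in treatment at 6 months?** A subject last seen on Day 106 had the last injection on Day 92, which is 169 − 92 = 77 days before EOT. A subject last seen on Day 120 or 134 had it at the latest on Day 120, 49 days before EOT. Counting them as retained would sit badly with Section 3.2 and with the synopsis.

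**Step 3: size, as an illustration only.** Assume a constant dropout hazard, S(t) = R^(t/169), where R is true attendance at Day 169. The exponents are 106/169 = 0.627 and 148/169 = 0.876.

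| | R = 30% | R = 50% | R = 70% |
|---|---|---|---|
| S(106) | 47.0% | 64.7% | 80.0% |
| S(148) | 34.8% | 54.5% | 73.2% |
| Counted as attending: S(106) − R | +17.0 | +14.7 | +10.0 |
| Same, if truth is attendance at the Day 148 injection visit: S(106) − S(148) | about +12 | about +10 | about +7 |
| Dropped as missing: R / (R + 1 − S(106)) | 36% | 59% | 78% |

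For the dropped row at R = 30%: 0.30 / (0.30 + 1 − 0.470) = 0.30 / 0.830 = 36%.

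If these subjects are instead censored in a Cox model, the latest stop that can be recorded is Day 92. The curve then stays at S(106), which again gives about 47/65/80%.

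**Step 4: would a 35-day rule alone be enough?** It leaves last visits on Day 148 unclassified. If those count as retained, the excess over Day 169 attendance is S(148) − R = 4.8, 4.5 and 3.2 points. If Day 134 is also left unclassified, it is 8.5, 7.7 and 5.4 points. A calendar rule reduces the problem but does not remove it.

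**The case against.** A reader might infer that late dropouts are scored as still attending, and that 6-month retention is therefore overstated. The documents do not say that. Section 14.8 says when a no-show is deemed to have stopped, not that everyone else is retained. The endpoint wording in Section 3.2 and the synopsis points the other way, since a subject absent after Day 106 does not satisfy it. The Section 14.8 sentence is also attached to a duration, whereas Section 14.7.2 analyses a binary status. This objection stands: the scoring is undefined, not defined wrongly.

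Nor is Section 14.8 the only rule on leaving treatment. Sections 6.4.4 and 10.1.1 catch last visits on Days 106 and 120. Section 6.4.1 records the reason for treatment withdrawal and, except for subjects lost to follow-up, provides monthly calls on treatment status. Section 6.3.1 defines completers by the EOT visit. That stands too, but it supplies a competing rule and does not tell the analyst which one governs the endpoint.

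The boundary needs care. If Day 106 is the first missed visit, five visits remain and the rule is just met on Day 169. A reading that excludes EOT from the count would extend the gap to last visits on Day 92, but the protocol calls EOT a visit throughout.

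Finally, the planned comparison is intravenous versus non-intravenous among treated subjects. Misclassification may fall in both groups, and nothing in the documents fixes its direction or size in that contrast. The primary endpoint is untouched.

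**Conclusion.** Wrong as written. The Section 14.8 rule cannot be met by anyone last seen on Day 106 or later, and it contradicts Sections 6.4.4 and 10.1.1 about the same subjects. Their 6-month status is not stated anywhere. This follows from the schedule alone and needs no assumption about dropout.

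The size is conditional. Counting these subjects as attending, or censoring them, inflates 6-month retention by about 17/15/10 points when true Day 169 attendance is 30/50/70%. Against attendance at the Day 148 injection visit, the excess from counting them as attending is about 12/10/7 points. Dropping them as missing inflates it by about 6/9/8 points (36 − 30, 59 − 50, 78 − 70). These figures rest on an assumed constant hazard and assumed retention levels. Of the options considered, only scoring them explicitly as not retained avoids the excess over Day 169 attendance, and the plan does not say to do so. No claim is made that retention will in fact be overstated, or that the intravenous contrast is biased in a known direction.

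**What to change.** 1. Reconcile Section 14.8 with Sections 6.4.4 and 10.1.1, so that the analysis uses one calendar-based rule with the stop date at the last attended visit. This concerns the analysis definition only, not when a subject should leave treatment.
2. In Sections 3.2 and 14.7.2, define the binary 3- and 6-month status directly from visit and injection records, using one pre-specified definition. Attendance at EOT and receipt of the injection scheduled at Visit 19 (Day 148) are both possible for 6 months, but they class some subjects differently, so one must be chosen before the data are seen.
3. State that all other subjects in the Treatment Population are scored as not retained, so that the no-imputation entry in Table 2 cannot remove them from the denominator.
4. Use the same definition in the synopsis, which at present describes the endpoint and its model differently.

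The cost is about a paragraph in Section 14.8 and matching sentences elsewhere. No new data are needed. The downside is that the reported 6-month retention may be lower.
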